Diabetic retinopathy (DR) is a complication of diabetes and a leading cause of blindness in adults as early as age 20. Youth with type 1 and type 2 diabetes are at risk for DR, yet only 35-72% of youth undergo recommended DR screening exams, with minority youth and children from lower socioeconomic backgrounds less likely to undergo screening as compared to their white counterparts.¹

Early detection of diabetic retinopathy through screening prevents progression to vision loss. While DR screening is traditionally fulfilled by a referral to an eye care provider (ECP) for a dilated eye exam, use of nonmydriatic fundus cameras with new and innovative autonomous artificial intelligence (AI) systems have recently been developed for DR screening. Autonomous AI performed at the point-of-care (POC) provides an immediate result, and was FDA approved for use in adults in 2018.² Autonomous AI technology has been validated against patient outcome, demonstrating an 87% sensitivity and 90% specificity in detecting referable DR in adults,² compared to 30-40% sensitivity for clinical experts,³ with equal safety and effectiveness for all races, ethnicities and ages, and higher diagnostic accuracy than clinical experts for detecting DR and DME. In a pilot prospective study at our pediatric diabetes center using AI technology for DR screening, we demonstrated 85.7% sensitivity and 79.3% specificity in detecting referable diabetic retinopathy, and an improved adherence to screening from 49% to 95%.⁴

We hypothesize that POC autonomous AI in the diabetes care setting will increase DR screening rates in youth with diabetes and mitigate disparities in access to screening. In this study, we will determine if point of care autonomous AI improves screening adherence compared to standard in person eye care professional exams in a randomized control trial.

A2 Primary Hypothesis

We hypothesize that POC Autonomous AI screening will increase DR screening rates in comparison to ECP (Aim 1a), and will improve follow-up with ECP in the case of abnormal findings (Aim 1b).

A3 Purpose of the Study Protocol

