We will perform a randomized control trial to determine if autonomous AI increases DR screening rates in comparison to ECP. ECP-based dilated eye exams are the standard of care, and thus will serve as the control arm in this study. Autonomous AI is an acceptable comparator, because it has been validated against patient outcome in the adult diabetes population,^{2,5} and data from a pilot study using autonomous AI off-label in pediatrics demonstrated diagnostic accuracy, and sufficient sensitivity and specificity for detection of DR in the pediatric population.⁴ The alternative strategy that we considered was telemedicine or teleretinal networks, which have been used for more than 20 years, but these systems have not been validated against patient outcome (ETDRS). Further, while reading centers have demonstrated consistent fundus image interpretation, the real-world use of networks with various trained readers (optometrists, ophthalmologists

and retina specialists) can result in variable interpretation.³ Thus we have chosen to compare autonomous AI to ECP.

B Study Objectives

B1 Primary Aim

To determine if point-of-care autonomous AI improves screening adherence compared to standard in-person eye care professional exams in a randomized control trial.

B2 Secondary Aim

To assess follow-up rates with ECP in the standard of care arm, compared to participants in the AI arm who screen positive and receive a referral to ECP for further evaluation.

C Study Design

C1 Overview of Study Design

This is a hypothesis-driven, pre-registered, prospective parallel, randomized control trial with a 1:1 allocation ratio where participants will be randomized to the standard of care or the autonomous AI arm.

The control arm is the standard of care referral to an eye care provider for a diabetic eye exam. In this study, to add *rigor, ethics* and maximum follow-up at ECP, participants in this arm will receive a scripted, brief educational intervention including the following 3 points: a) risks for complications of diabetes, b) what a DR screening exam entails and where it can be done, and c) reminder to have results faxed to their endocrine provider. We propose that this addresses the ethical concern of poor baseline completion of the diabetic eye exam amongst people with diabetes.

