In the intervention arm, or autonomous AI arm, participants will undergo point of care diabetic eye exams using autonomous AI in the pediatric diabetes clinic, and will receive immediate results from autonomous AI. If the screen is normal, they have completed their screening. If the AI screen is abnormal, they will then be referred to ECP for further examination and will receive a scripted educational intervention. If the images are insufficient for interpretation, they will be referred to ECP for further examination and will receive a scripted educational intervention.

Followup: After randomization in the study, participants will have 6 months to complete the diabetic eye exam (in the control arm) or follow-up eye exam (in the intervention arm if AI abnormal). If the exam is not complete by 6 months, or the participant cannot be reached to determine completion of the exam, it will be considered not done.

C2 Subject Selection and Withdrawal

2.a Inclusion Criteria

- T1D: 11 years of age or older or in puberty, with diabetes for at least 3 years (ADA guidelines)⁶
- T2D: at diagnosis and thereafter (ADA guidelines)
- No known diabetic retinopathy
- No diabetic retinopathy exam within the last 6 months

2.a Exclusion Criteria

- Known diabetic eye disease

2.b Subject Recruitment Plans and Consent Process

Individual(s) responsible for approaching participant(s): Research coordinators

Where and when recruitment will take place:

Participants will be recruited, screened for eligibility, and consented in a private clinic/room to ensure privacy.

Consent process:

Participants will read through the consent form with the research coordinator, have time to review it and ask questions about the study and study procedures.

2.c Randomization Method and Blinding

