- 2) **Autonomous AI.** Participants in the intervention arm will undergo POC DR screening using autonomous AI in the pediatric diabetes clinic, and will receive immediate results from autonomous AI. If the screen is normal, they have completed their screening. If the AI screen is abnormal, they will then be referred to ECP for further examination and will receive a scripted educational intervention stating the importance of eye care follow-up and to have results faxed to their endocrine provider. If the images are insufficient after 3 attempts, then they will be referred for eye care follow-up.
 - a. Participants in the AI arm will complete a survey after the AI eye exam is complete.
- 3) **Follow-up:** Participants will have up to 6 months to complete the ECP diabetic eye exam (control arm) or follow-through eye exam after an abnormal AI result in the intervention arm.

Children with diabetes care are typically seen by their diabetes provider every 3 months. As part of routine diabetes intake, patients are asked if they have had an eye exam since the last visit and the date is recorded by the nurse or diabetes provider.

If a participant returns for diabetes care to the clinic within the 6-month follow-up window, and an eye exam is reported, the research coordinator will meet with the participant to complete a follow-up acceptability survey (paper and pencil or on a tablet). If the eye exam results are not in the medical chart, the research coordinator will contact the eye doctor's office to have the results faxed to the provider office.

Once the participant reaches their 6-month follow-up window and there is no documentation of the eye exam in the medical record, the study coordinator will approach the participant in person at the next diabetes clinic visit to determine if they completed an ECP visit, or contact the family by EHR-based secure messaging, or calls / voicemails to all 3 phone numbers provided upon enrollment. The eye exam will be considered complete if documentation of the eye exam is in the medical record, or the participant/caregiver reports the diabetic eye exam completed.

If the exam has not been completed by 6 months or the participant cannot be reached, it will be considered not done/unscreened.

D3 Autonomous AI diabetic eye exam procedure

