The secondary outcome is follow-up at ECP in each arm, comparing proportion of participants who arrive at ECP for DR screening in the control arm, to the proportion of participants in the AI arm who have an abnormal AI screening, are referred to ECP for follow-up, and arrive at ECP. This will be analyzed using a Pearson's chi-square test and logistic regression (adjusting for covariates).

E3. Statistical Methods

Statistical analyses will be performed using Stata 15.1 (Statacorp, College Station, TX). The primary and secondary outcomes will be further analyzed (in addition to above) using multivariate logistic regression analyses in order to examine the relationship between demographic characteristics and the outcomes. Additionally, multivariable logistic regression analyses will assess the odds of having a previous diabetic eye exam, adjusting for known covariates associated with diabetic eye disease. This will be an intent to treat analysis; all participants will be analyzed.

E4. Missing Outcome Data

Dataset will be assessed for missing-ness and noted in results.

E5. Unblinding Procedures

Not applicable

F. Data Handling and Record Keeping

F1. Confidentiality and Security

All data for this study will be recorded and stored in REDcap through Johns Hopkins Medicine.

F2. Records Retention

Informed consent documents will be securely stored in a locked file cabinet within a locked office. Informed consents will also be scanned into the participant's electronic medical record. Eye exam results from the AI camera will be uploaded into the Media section of the participant's electronic medical record in Epic.

G. Study Administration

G1. Organization and Participating Centers

Johns Hopkins Pediatric Diabetes Center
Mount Washington Pediatric Hospital Diabetes Center

G2. Funding Source

Funding for this study is provided by the National Eye Institute of the National Institutes of Health under Award Number R01EY033233 (PI: [name]), and the Diabetes Research Connection (PI: [name]).

G3. Subject Stipends or Payments

Participants received a \$25.00 gift card, and a parking pass at the study visit.

E References

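### The Aim 1b test compares all controls with AI-positives, a group formed after randomisation in one arm, so a significant p-value cannot by itself support the claim in A2 that AI improves follow-up

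*Combined protocol and SAP*

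**What the plan says.** Section A2, headed as the primary hypothesis, states that point-of-care AI screening "will improve follow-up with ECP in the case of abnormal findings (Aim 1b"). B2 puts the secondary aim more neutrally: "To assess follow-up rates with ECP in the standard of care arm, compared to participants in the AI arm who screen positive" and are referred.

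The secondary-outcome paragraph of E3 (Analysis Plan) turns this into a test. On the control side it takes the "proportion of participants who arrive at ECP for DR screening in the control arm". On the AI side it takes "the proportion of participants in the AI arm who have an abnormal AI screening, are referred to ECP for follow-up, and arrive at ECP". The methods are Pearson's chi-square and logistic regression with covariates that are not named. E3 (Statistical Methods) adds regressions to "examine the relationship between demographic characteristics and the outcomes".

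C1 gives participants six months to "complete the diabetic eye exam (in the control arm) or follow-up eye exam (in the intervention arm if AI abnormal"). D2 adds a third route to the ECP in the AI arm: "If the images are insufficient after 3 attempts, then they will be referred for eye care follow-up". The E3 secondary outcome does not mention these participants. Nothing in the document calls the Aim 1b contrast descriptive or non-randomised.

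**The concern.** The hypothesis in A2 is about what people do once there is an abnormal finding. To test it as a randomised effect, one would need follow-up among participants with abnormal findings in both arms. The plan has that in the AI arm only.

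Three features separate the two sides of the test:

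- **The group.** AI-positives are selected by a test taken after allocation, which controls do not take. Randomisation balances the arms as wholes. It does not balance a result-defined part of one arm against all of the other.
- **The event.** Controls attend for a screening exam. AI-positives attend for work-up of a result they have just been told is abnormal, after a different script (D2).
- **What is observed.** A control's retinal status becomes known only through an ECP exam. D2 provides for retrieving those results ("If the eye exam results are not in the medical chart, the research coordinator will contact" the eye doctor's office), but only once an exam has been reported. A control with an abnormal retina who does not attend is never identified.

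What is at stake is the conclusion. Because Aim 1b stands beside Aim 1a in A2, a small p-value could be reported as trial evidence that AI improves follow-up.

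**Working it through.** **1. The plan's own sample size.** E1 gives 60% against 80% (a 20-point difference), two-sided 0.05, 80% power, 1:1. With the pooled-variance formula, n per arm = [1.96·√(2·0.7·0.3) + 0.8416·√(0.6·0.4 + 0.8·0.2)]² / 0.2² = 81.2, so 82 per arm and 164 in total, as stated. This sizes the primary outcome. No calculation is given for Aim 1b.

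**2. How many AI-positives.** A1 gives two accuracy pairs for referable retinopathy: 85.7% sensitivity and 79.3% specificity (paediatric pilot), and 87% and 90% (adults). Prevalence is not in the document; 0-20% is an assumption. With all images gradable, the positive rate is q = sens·prev + (1 − spec)·(1 − prev).

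| Prevalence | Pilot: q, positives of 82 | Adult: q, positives of 82 |
|---|---|---|
| 0% | 0.207, 17.0 | 0.100, 8.2 |
| 5% | 0.240, 19.6 | 0.139, 11.4 |
| 10% | 0.272, 22.3 | 0.177, 14.5 |
| 20% | 0.337, 27.6 | 0.254, 20.8 |

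**3. Can the test reach significance?** Take 49/82 controls attending (E1's assumed 60%) and Pearson's test without correction. With 20 positives, 16/20 gives p=0.091, 17/20 gives p=0.034 and 18/20 gives p=0.011. With 8 positives, 7/8 gives p=0.12 and 8/8 gives p=0.024. A nominally significant result is attainable, though with few positives only near-complete attendance reaches it.

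**4. Selection alone, with no AI effect.** Let attendance be 60% overall and aD among youth with retinopathy; aD is assumed. Then:

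- attendance without retinopathy: aN = (0.60 − prev·aD)/(1 − prev)
- PPV = sens·prev/q
- attendance in AI-positives = PPV·aD + (1 − PPV)·aN

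Example (pilot, 10% prevalence, aD = 90%): aN = (0.60 − 0.09)/0.90 = 0.567; PPV = 0.0857/0.272 = 0.315; attendance = 0.315·0.90 + 0.685·0.567 = 0.672, against 0.60 in controls.

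The table gives exact two-sided rejection rates at 0.05, with 82 controls at 60% and the rounded number of positives.

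| aD | Pilot, prevalence 5/10/20% (20/22/28 positives) | Adult, prevalence 5/10/20% (11/15/21 positives) |
|---|---|---|
| 40% | 5.8 / 7.2 / 11.5% | 6.8 / 10.4 / 17.9% |
| 60% | 5.1 / 5.1 / 5.2% | 4.9 / 5.1 / 5.2% |
| 80% | 5.5 / 6.6 / 10.9% | 5.6 / 8.9 / 16.7% |
| 90% | 6.1 / 8.9 / 19.0% | 7.0 / 14.7 / 33.5% |

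At aD = 40% the rejections go mostly against AI; at 80% and 90% they mostly favour it. If attendance is unrelated to disease, the test keeps about its 5% level.

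**5. What the arithmetic leaves out.** The model treats both visits as the same event. They are not, so even the 60% row, with no selection bias, would not turn the contrast into a measure of follow-up after abnormal findings in both arms.

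**The case against.** The strongest defence is that comparing referral completion under two strategies is a legitimate question. Being told of an abnormal result is how AI would raise attendance, so the different reason for the visit is partly the intervention rather than a confounder. That stands, and it is why both proportions are worth reporting. It does not make the contrast a randomised one.

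Other points also stand in part:

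- **B2.** A reader might infer that B2 makes the same causal claim as A2. It does not: it sets out to assess rates and predicts no improvement.
- **Adjustment.** A reader might infer that no control counterpart could ever be constructed, or that regression is useless because controls have no AI result. That is too strong. Baseline predictors of a positive result can be learned in the AI arm and used to weight or adjust controls, and E1 shows that prior-exam rates differ by race (46% and 85%). But this needs the untestable assumption that those predictors capture the selection. The plan names no covariates, and no adjustment makes the two events the same.
- **Size.** A reader might infer a badly inflated false-positive rate. The document supports no such figure. Known retinopathy is excluded, so participants do not know their status, and no reason is given why undiagnosed disease should raise attendance to 80% or 90%.
- **Denominator.** Read alone, E3 could mean a proportion of the whole AI arm. A2, B2 and C1 point to AI-positives, so this needs one clarifying line and is not a separate flaw.
- **Rank.** The outcome is secondary, and how it will be reported is a prediction.

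**Conclusion.** The point holds as a limit on what may be concluded. The E3 contrast for Aim 1b is not protected by randomisation, and follow-up after an abnormal finding is not measured on a comparable basis in controls. A significant p-value therefore cannot by itself support the improvement stated in A2. This conclusion rests on the text of A2, B2, C1, D2 and E3, not on the modelled figures.

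The figures show only how far disease-related selection might distort the test, under assumed prevalence and attendance. With the pilot accuracy, rejection is about 5-9% at 5-10% prevalence; with the adult accuracy it is up to about 15%. At 20% prevalence it is about 11-18% when diseased youth attend at 40% or 80%. It reaches 19% (pilot) or about a third (adult) only when 20% prevalence is combined with 90% attendance. The bias can go either way and may be modest.

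A reader might infer that the main result is also compromised. It is not: the primary outcome compares the arms as randomised. The change should be made, but it does not threaten the trial's main conclusion.

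**What to change.** In E3:

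- State the denominator as AI-arm participants with an abnormal AI result who are referred to ECP, in line with B2.
- Report their ECP attendance by six months as a proportion with a 95% confidence interval. For example, 16/20 would be 80% with a Wilson interval of 58-92%.
- Report attendance among participants referred for insufficient images as a separate proportion, outside that denominator.
- Label any contrast with the control arm as non-randomised and descriptive.

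In A2, reword Aim 1b so that it claims no randomised improvement, for instance: to describe ECP attendance after an abnormal AI result, alongside ECP attendance in the control arm. B2 needs no change.

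The cost is wording in two sections and no new data. The sponsor gives up a causal reading of this secondary contrast. The primary comparison and N=164 stay as they are.

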The following power calculations assume 80% power and a 2-tailed type 1 error of 0.05. Data from the pilot study in pediatrics showed that of all children in the study, only 49% reported a prior diabetic eye exam, and this increased to 95% with the implementation of POC AI screening.⁴ National data show that 42% of youth with T2D and 66% of youth with T1D had a diabetic eye exam by 6 years after initial diabetes diagnosis,¹ and our preliminary data showed that of youth who met ADA criteria for DR screening, 66% had a prior diabetic eye exam (46% non-white, 85% white youth). We assume that adding the educational intervention will raise the ECP rate to 60%. Randomization and study visit occur at the same time so there is little risk of attrition, and thus the study sample size will not be expanded to account for attrition. To show difference in proportion of who gets screened we assess a 20% difference to be clinically relevant between the two

strategies. Committing to demonstrating this difference results in a sample size of 164 (n=82 ECP, n=82 AI).

E2. Interim Monitoring and Early Stopping

One interim efficiency analysis for efficacy is planned. Using the alpha spending function with O'Brien and Fleming stopping rules, we will stop the trial if we show efficacy at the $p < 0.0054$ level. To adjust for the interim look, if the trial continues to the planned full sample size, the threshold for significance will be $p < 0.0492$.

Although consideration may be given to stop the study early because of an apparent beneficial treatment effect, early termination for efficacy will be considered with caution because of the degree of uncertainty with regard to the long-term benefit of treatment even if a short-term benefit seems apparent prior to the completion of the study. This will be determined by the independent DSMB committee.

E3. Analysis Plan

Primary outcome variable.

The primary outcome is the *proportion* of participants who get screened between AI and ECP. The comparison will be assessed using a Pearson's chi-square test (primary outcome) and logistic regression (adjusting for covariates).

Secondary outcome variables.

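### Does the A1 statement that AI will reduce screening disparities require a named arm-by-group contrast in E3?

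*Combined protocol and SAP*

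**What the plan says.** A1 describes the background problem as uneven uptake, "with minority youth and children from lower socioeconomic backgrounds less likely to undergo screening as compared to their white counterparts", and hypothesises that point-of-care AI "will increase DR screening rates in youth with diabetes and mitigate disparities in access to screening". The sentence that follows sets the trial's own task: "In this study, we will determine if point of care autonomous AI improves screening adherence compared to standard in person eye care professional exams". A2 lists a screening-rate hypothesis (Aim 1a) and a follow-up hypothesis (Aim 1b). B1 is "To determine if point-of-care autonomous AI improves screening adherence compared to standard in-person eye care professional exams", and B2 concerns follow-up with the eye care provider. None of A2, B1 or B2 mentions disparities.

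E1 gives the team's preliminary figures: "66% had a prior diabetic eye exam (46% non-white, 85% white youth". E3 (Analysis Plan) specifies a chi-square test and covariate-adjusted logistic regression for each outcome. E3 (Statistical Methods) adds regression "using multivariate logistic regression analyses in order to examine the relationship between demographic characteristics and the outcomes", without listing the characteristics or the terms. A further model there concerns having had a previous eye exam, which is history and not a trial outcome.

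**The concern.** A1 introduces the disparity statement as a hypothesis, and E1 puts a 39-point racial gap (85% minus 46%) beside the design assumptions. A reader then expects E3 to say how a change in that gap would be estimated. It names no arm-by-group contrast, no grouping and no scale. A pooled model with arm and group as main effects only would report an average demographic association, not whether AI alters it. Any later statement that AI reduced disparities could then rest on a model, grouping and scale chosen after the data were seen. The scale matters: a gap can narrow in percentage points while the odds ratio stays the same or widens.

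**Working it through.** **1. The plan's own figure.** E1 assumes 60% versus 80%, two-sided 0.05 and 80% power. With pooled variance, n per arm = [1.96·√(2·0.7·0.3) + 0.8416·√(0.24 + 0.16)]² / 0.20² = (1.270 + 0.532)² / 0.04 = 81.2, so 82 per arm and 164 in total. This agrees with E1. The design is sized for the overall comparison, and nothing below alters it.

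**2. Inputs for the disparity question (assumptions built on E1).** The non-white share w solves 0.66 = 0.46w + 0.85(1 − w), so w = 0.19/0.39 = 0.487; use 41 non-white and 41 white per arm. Control is 60% overall. If the 39-point prior-exam gap carried over, the control cells would be 40.5% and 79.5%. AI is 80% (design) or 95% (pilot).

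**3. What a pooled main-effects fit can and cannot show.** Its estimates depend only on arm and group totals. Rates below are non-white/white, with AI at 80% overall:

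| Pattern | Control | AI | Arm OR | Non-white OR |
|---|---|---|---|---|
| Gap closed | 40.5/79.5 | 80/80 | 2.80 | 0.37 |
| 19.5-point gap in both arms | 50.25/69.75 | 70.25/89.75 | 2.80 | 0.37 |
| Odds ratio unchanged | 48.2/71.8 | 72.3/87.7 | 2.80 | 0.37 |

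The match is exact because the control gap is varied (39, 19.5 and 23.6 points) to hold the totals fixed. If the control gap is held at 39 points, the non-white OR is 0.37 with the gap closed, 0.21 with it halved (70.25/89.75) and 0.10 with it unchanged (60.5/99.5). So a pooled coefficient is uninformative only when the control gap is not examined separately. E3 does not commit the analyst to a pooled fit.

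**4. What a named contrast would deliver.** Contrast = (white − non-white in control) − (white − non-white in AI); SE = √Σ p(1 − p)/n over the four cells.

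- AI 80%, 39 points closed: SE = √[(0.2410 + 0.1630 + 0.16 + 0.16)/41] = 0.133. The 95% half-width is 26 points and power is Φ(0.39/0.1329 − 1.96) = 83%. On the log-odds scale (1.740, SE 0.745) power is 65%.
- AI 80%, 39 points halved: SE 0.131, power Φ(0.195/0.1311 − 1.96) = 32%. On log odds (0.429, SE 0.795) power is 8%.
- AI 95%, 39 points closed: SE 0.110, half-width 22 points, power 94%. On log odds (SE 1.130) power is 34%.
- With 25 of 82 non-white and AI at 80%, the half-width is 29 to 30 points.

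**5. Scale.**

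- The control odds ratio at 40.5/79.5 is (0.795/0.205)/(0.405/0.595) = 5.70. Held unchanged with AI at 95% overall, it gives 91.6/98.4, a gap of 6.8 points. The contrast is 39 − 6.8 = 32 points with SE 0.110 and power 83%, although nothing has changed on the odds scale.
- The odds-ratio term is a weak check there: with AI at 95% its uncertainty is a factor of 9 or more either way.
- The scales can also disagree in direction. From 46/85 to 66/95 the gap falls from 39 to 29 points, while the odds ratio rises from 6.65 to 9.79.

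**The case for a change.** The strongest case for a change is that A1 states the clause as a hypothesis, C1 describes the trial as driven by hypotheses and registered in advance, and the trial will hold the four arm-by-group cells if race is recorded. A few sentences in E3 would remove a post-hoc choice of grouping, model and scale at no cost in visits or participants. A large closure would be detectable in points (83% to 94% under step 4).

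Much of this is correct. The regression is under-specified for a disparity statement, and a pooled main-effects coefficient should not be cited as evidence that AI narrowed the gap. What it does not show is an error in the plan. The clause is not carried into any aim, and the demographic regression can be fitted within arm or with an interaction without departing from E3. Logistic regression already implies an odds-ratio scale. Leading with points would be a preference with its own cost, since with AI at 95% and equal groups the AI-arm gap cannot exceed 10 points (90/100), so a 39-point control gap must shrink by at least 29 whatever the mechanism.

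**Conclusion.** No change is needed. Following E3 as written gives no wrong result for either declared outcome; the sample size reproduces, and the primary and secondary comparisons do not depend on this point. What is missing is detail for an exploratory reading of a background statement. Analysts can supply it by showing the four cell proportions and treating any arm-by-group estimate as exploratory. The gain from fixing it now is small: half-widths of about 22 to 30 points, and 32% (points) or 8% (log odds) power for a halved gap. The choice of lead scale is a genuine trade-off with no clear winner.

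These figures rest on assumptions. The 46%/85% gap is prior-exam history, not six-month completion after the educational script. The near-even mix is back-calculated from preliminary data. The plan does not list which demographic characteristics are recorded. The conclusion itself rests on the scope set in A2, B1 and B2 and does not depend on those rates.
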